### **Potential benefits to patients**

All patients will continue to receive their existing background anti-hyperglycaemic therapy and the study protocol allows other existing therapies to be optimized before randomization to ensure that participants will receive optimal treatment according to country specific and/or regional guidelines. However, a direct benefit from randomised treatment cannot be assured as one half of patients are expected to receive placebo. The expectation, based on previous

Phase III studies, is that treatment with dapagliflozin is likely to improve glycaemic control (the extent however remains to be determined) because the effect does not seem to depend on age or CV risk factors as can be judged from previous data, and only moderate renal impairment is allowed. In this study, the dose of dapagliflozin (10 mg) has been chosen to provide efficacy in reducing hyperglycaemia while providing the best balance of benefit versus risk based on available information from previous studies. In addition, dapagliflozin is expected to decrease body weight (the extent of which needs to be determined) as well as lower blood pressure especially in patients with elevated baseline blood pressure. Furthermore, all patients including those who receive placebo treatment are expected to experience a benefit in the form of increased medical care/attention when participating in study procedures, which include at least 18 clinic visits with at least 17 physical examinations over the course of this 112-week study. Patients will also receive counselling for dietary and lifestyle modifications. It is commonly observed that even patients receiving placebo in diabetes studies show some improvement in glycaemic control, likely due to their increased compliance to dietary and lifestyle counselling while they are participating in a clinical study. Rescue criteria for hyperglycaemia and hypertension have been defined according to guidelines in order to ensure adequate treatment for the participants.

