**Table 4**            **Efficacy variables with related objectives and rationale**

Efficacy variable	Related objective	Rationale
HbA1c	
Change in HbA1c compared to baseline at week 24.
 
Change in HbA1c in patients with baseline HbA1c <math>\geq 8\%</math> and HbA1c <math>\geq 9\%</math> at week 24.
 
Proportion of patients achieving a therapeutic glycaemic response defined as HbA1c <math>< 7.0\%</math> at week 24.
 
Proportion of patients achieving a therapeutic response defined as a reduction in HbA1c of 0.5% or more at week 24.
	
HbA1c is the clinical and regulatory parameter used to estimate glycaemic efficacy in patients with type 2 diabetes. HbA1c targets for patients with type 2 diabetes range from <math>< 6.5\%</math> to <math>< 7.0\%</math> and ADA and EASD recently reached consensus on an HbA1c treatment target of 7.0% (Nathan et al 2009). The degree of change in HbA1c in patients with type 2 diabetes is related to the baseline HbA1c level; patients with higher HbA1c at baseline tend to have greater reductions in HbA1c when treated with any anti-hyperglycaemic agent.

Efficacy variable	Related objective	Rationale

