The second primary efficacy variable, proportion of patients at week 24 who meet all criteria of a 3-item clinical benefit composite, will be analyzed by the Cochran-Mantel-Haenszel (CMH) method. When assessing the results overall, the CMH model will include age-by-insulin use-by-time from most recent qualifying CV event group as a strata variable. To help characterize the treatment effect, a secondary test for homogeneity of treatment effect between age strata will be performed at the 0.10 level of significance; however, the results of this test will not alter the conclusion of the previously specified model since the effect of dapagliflozin versus placebo will be examined in each age stratum separately. When assessing results within each age stratum, the CMH model will include insulin use-by-time from most recent qualifying CV event as a strata variable. The difference in response rates between dapagliflozin and placebo will be displayed along with a 95% confidence interval derived from asymptotic theory. P-values will be calculated from a chi-square test using the appropriate CMH model described above. If there are less than 5 responders on average by treatment group, an exact 95% confidence interval will instead be calculated along with the p-value from Fisher's exact test.

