The proportion of patients achieving therapeutic glycaemic response, defined as HbA1c <7.0%, at week 24 will be analyzed using the methodology of [Zhang et al 2008](#) and [Tsiatis et al 2007](#) when there are at least 5 responders on average by treatment group. For proportion of responders, estimates, confidence intervals, and tests will be obtained using this methodology with adjustment for baseline HbA1c and age group. For each treatment group, the probability of response is first modelled using a logistic regression model with baseline HbA1c as the covariate. Treatment group estimates of response rate are then obtained by integrating each group's modelled probability of response over the observed distribution of baseline covariate (combined across groups). The difference in response rate between dapagliflozin and placebo will be displayed along with the 95% confidence intervals. P-values will be calculated (when applicable). When there are less than 5 responders on average by treatment group, the unadjusted proportions and difference between unadjusted proportions, exact 95% confidence interval, and p-values from the Fisher's exact test (when applicable) will be provided. Analyses will also be conducted separately within each age stratum. The same method will be applied for analyzing other proportions of patients achieving a pre-defined response derived from a single variable, including the key secondary variable proportion of patients with baseline BMI  $\geq 27$  kg/m^2 with a reduction of 5% or more in body weight from baseline to week 24.

Other discrete variables will be summarized by counts, proportions and corresponding two-sided 95% confidence intervals for each treatment group overall and, where appropriate, within each age stratum. Comparisons between treatments will be performed using two-sided Fisher's exact test, when applicable.

The time course of all continuous variables will be presented using standard descriptive summary statistics calculated at each scheduled measuring time point and the last individual measuring time point. Moreover, standard descriptive summary statistics will be calculated for the change (absolute or percent) from baseline to each scheduled measuring time point after baseline and the last individual measuring time point. Analyses by subgroups, including

the stratification factors of insulin use and time from qualifying CV event, will be defined in the SAP.

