### 12.3 Determination of sample size

The sample size for this study was selected to be consistent with the research hypotheses as described in Section 1.2.

The study has two primary endpoints for which the overall probability of a Type 1 error (Family-wise error rate) will be strictly controlled at no more than 0.05 by testing each primary endpoint at a significance level  $\alpha=0.025$  in the overall population and 0.0125 within each age stratum. The sample size for this study is governed by the comparison with least power to achieve statistical significance; namely, for the within-age stratum comparison for the 3-item clinical benefit composite as explained below. Significance levels are expressed in terms of two-sided alternatives; however, all tests in practice will be performed against one-sided alternatives using one-half the significance levels reported here.

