From post-hoc results of a Phase III dapagliflozin study, when patients meeting entry criteria like those in this current study were selected, the proportion who successfully attained the 3-item clinical benefit composite endpoint after 24 weeks of treatment and who did not meet the rescue criteria in the current study was estimated to be 18.0% for dapagliflozin 10 mg (0% for placebo). The present trial seeks to detect a treatment difference over placebo of 15 percentage points within either age stratum with high statistical power (90%). Given patients will be randomised with equal probability to dapagliflozin or placebo, it follows that 362 patients (181 per group) will provide 90% power to detect a difference in responder rates of 25% versus 10% ( $\Delta=15\%$ ) within a given age stratum at a significance level  $\alpha=0.0125$  using a chi-square test. If 3.7% of randomised patients fail to qualify for inclusion in the full analysis set due to missing baseline and/or all post-randomization values for this primary endpoint, then a total of 376 randomized patients at minimum are required for each age stratum. Since it is permitted to randomize as few as 40% of the total patient population in one of the age strata, it follows that in order to ensure at least 90% power for the treatment comparison in the smaller age stratum, the larger age stratum must randomize 564 patients (60% of total). Therefore, with respect to the 3-item clinical benefit composite endpoint, 940 randomized patients in total are needed for the study. This sample size provides  $>99\%$  power to detect the same difference in the overall study population at a significance level  $\alpha=0.025$ .

With regard to the other primary efficacy variable, to detect a difference of 0.5% between dapagliflozin versus placebo for mean change in HbA1c from baseline to week 24, assuming a standard deviation (SD)  $\sigma=0.9\%$ , 181 evaluable patients (full analysis set) for each treatment group within a given age stratum would provide  $>99\%$  power for the analysis of each age stratum separately at a significance level  $\alpha=0.0125$  using a two-sample t-test. The estimate of

the SD for this calculation is based on data from the same study used to estimate proportion of patients attaining the 3-item clinical benefit noted above.

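### The composite co-primary, which sets the sample size, is adjusted for the randomisation strata but not for baseline HbA1c, systolic pressure or weight, unlike the other co-primary and the single-variable responder endpoints

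*Supplement*

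**What the plan says.** All of this is in protocol section 12.2.1 unless stated otherwise.

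- **Composite co-primary.** For the overall analysis, "the CMH model will include age-by-insulin use-by-time from most recent qualifying CV event group as a strata variable" (8 cells). Within each age group the strata are insulin use by time from the CV event (4 cells). The p-value comes from this CMH test. The displayed difference has a 95% interval described only as asymptotic, without saying whether it is crude or stratum-weighted. If responders average fewer than 5 per group, an exact interval and Fisher's test replace it.
- **HbA1c co-primary.** ANCOVA with the same strata plus the baseline value. Other continuous efficacy variables follow the same method.
- **Single-variable responders.** HbA1c below 7% is analysed by a logistic method fitted in each arm and averaged over the baseline distribution. Estimate, interval and test all come from that method. Then: "The same method will be applied for analyzing other proportions of patients achieving a pre-defined response derived from a single variable", including the key secondary 5% weight-loss endpoint. The covariate is spelled out only for HbA1c.
- **Why baseline matters.** Table 4: "The degree of change in HbA1c in patients with type 2 diabetes is related to the baseline HbA1c level". Section 1.4 expects dapagliflozin to "lower blood pressure especially in patients with elevated baseline blood pressure".
- **Sizing (section 12.3).** "The sample size for this study is governed by the comparison with least power to achieve statistical significance", which the plan identifies as the within-age test of the composite.

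**The concern.** The endpoint that fixes the size of the trial receives the least covariate adjustment of the responder endpoints, and no reason is given. Two of its three items, the HbA1c and systolic pressure drops, are ones whose response the protocol itself connects with the starting level. The baseline values are collected anyway.

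Three things are at stake:

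- **Precision.** An age stratum at the 40% floor has almost no spare power.
- **Chance imbalance.** With about 362 evaluable patients in such a stratum, a chance difference in baseline HbA1c or pressure moves the estimated difference, and CMH on the randomisation strata does not correct for it.
- **Matching estimate and test.** As written, the displayed difference and interval need not correspond to the stratified p-value.

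A composite that misses significance in one population also lowers the level for that population's key secondary sequence from 0.05 to 0.025.

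**Working it through.** **Inputs from section 12.3.** Responder rates 25% and 10%; 1:1 allocation; 90% power; 3.7% not evaluable; smallest age stratum 40% of the total. Alpha is 0.025 "in the overall population and 0.0125 within each age stratum". "Significance levels are expressed in terms of two-sided alternatives", and testing one-sided at half the level gives the same numbers.

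**Step 1: reproduce the plan.** Unadjusted chi-square, pooled variance, no continuity correction:

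n per arm = [z(0.99375)·√(2·0.175·0.825) + z(0.90)·√(0.25·0.75 + 0.10·0.90)]² / 0.15²
= [2.498·0.5374 + 1.282·0.5268]² / 0.0225 = 180.9, so 181.

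Then 2 × 181 = 362; 362/0.963 = 376; 376/0.40 = 940. Power at 181 per arm is 90.03%. Every stated figure reproduces.

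**Step 2: what adjustment could gain.** The documents do not give the share of outcome variance (R²) that the baseline values explain beyond the strata. Assume a range and use effective n = n/(1 − R²). The 226 per arm is the planned equal split: 470 × 0.963 / 2.

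| Assumed R² | Power, 181 per arm (40% floor) | Total N for 90% at the floor | Power, 226 per arm (equal split) |
|---|---|---|---|
| 0 | 90.0% | 940 | 95.8% |
| 0.02 | 90.7% | 925 | 96.2% |
| 0.05 | 91.7% | 895 | 96.7% |
| 0.10 | 93.2% | 848 | 97.5% |
| 0.15 | 94.6% | 800 | 98.2% |

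**Step 3: which part of that range is plausible.** Simulations at 181 per arm generated the three components. They assumed a correlation of baseline with change of −0.25 to −0.5 for HbA1c and −0.3 to −0.55 for systolic pressure. The change SD for HbA1c was the plan's 0.9; the other component SDs were assumed.

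- CMH 90.7%, 90.4%, 91.3% against pooled logistic standardisation 91.7%, 91.8%, 93.4%: gains of 1.0, 1.4 and 2.1 points.
- A separate simulation: 90.2% to 90.9%, 91.1% to 92.2%, 92.4% to 94.0%: gains of 0.7, 1.1 and 1.6 points. At about 226 per arm the change was within 1 point either way.
- Counting high on-treatment pressure as rescue, hence non-response: 90.3% to 90.7% and 91.6% to 93.3%.

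These gains correspond to the lower part of the table. Type I error of the adjusted analysis stayed near the nominal 0.0125 (0.9% to 1.5%, Monte Carlo error about 0.25 points).

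**Step 4: chance imbalance.** In the same simulations the unadjusted difference moved 0.3 to 0.6 points per SE of imbalance in systolic pressure and 0.3 to 0.45 per SE in HbA1c. After adjustment it moved about 0.1 per SE or less. An imbalance of 2 SE in both, in the same direction, gives 2 × (0.3 + 0.3) = 1.2 to 2 × (0.6 + 0.45) = 2.1 points. The SE of the difference is √[(0.1875 + 0.09)/181] = 3.9 points, so this is about a third to a half of one SE.

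**Step 5: sparse data.** Section 12.3 cites post-hoc rates of 18% on dapagliflozin and 0% on placebo. At 181 per arm that is 0.18 × 181 ≈ 33 responders against 0, an average of about 16 per group. The existing rule, fewer than 5 on average, would not trigger. Yet a logistic model with no placebo responders separates on treatment.

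**The case against.** The case for leaving the plan alone is substantial, and much of it stands.

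- A reader might infer that the composite has no baseline adjustment at all. The CMH sentence rules that out: age group, insulin use and time from the event are all baseline factors.
- A reader might infer a biased or underpowered test. The documents do not support this. The trial was sized on an unadjusted chi-square, the analysis matches, and stratified CMH is valid under randomisation. Chance imbalance is part of what the interval already covers, and 2 SE in both covariates in the same direction has a probability of about 0.1% if they are independent.
- A reader might infer that the protocol calls baseline a strong predictor. It does not. Table 4 says only that change and baseline HbA1c are related, and section 1.4 states an expectation about the drug's own effect on pressure, not about response in both arms.
- The composite is not the only efficacy proportion without a baseline covariate. Other discrete variables go to Fisher's exact test.
- The protocol's per-arm logistic method would be fragile here: the planning case gives about 18 placebo responders per stratum (0.10 × 181).
- Section 12 promises a SAP, which is not among the documents reviewed. It may already hold a supportive adjusted analysis or the interval formula.

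What remains is a difference in method for the endpoint that governs the sample size, with no stated reason, and an improvement that needs only wording.

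**Conclusion.** The composite should be given an analysis that uses the baseline values of its components. This is an efficiency and consistency improvement, not the repair of an invalid test. The gain is roughly 1 to 2 power points in a stratum at the 40% floor, could be close to nil if rescue absorbs much of the baseline pressure effect, and is smaller at the equal split, where power is already about 96%. Overall power at 0.025 is 99.99% and is not in question. The second benefit is less movement of the estimate under chance imbalance. Both sizes rest on assumed correlations that the documents do not give. The mismatch between displayed difference and test needs no such assumption: on the protocol text, the two are not tied together.

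**What to change.** Before unblinding, pre-specify in the protocol or SAP:

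1. **Model.** One pooled logistic model with treatment, randomisation stratum (8 levels overall, 4 within age), baseline HbA1c, baseline seated systolic pressure and baseline weight, standardised to a risk difference. Estimate, interval and p-value all come from this model.
2. **Role.** Make it primary with CMH as supportive. At minimum, keep CMH primary and name the adjusted model as supportive.
3. **Sparse-data rule.** If either arm, not the average of the two, has fewer than a pre-set number of responders, revert to stratified CMH, or to Fisher's exact test under the existing rule.
4. **Display.** Wherever CMH is used, show the Mantel-Haenszel stratum-weighted risk difference and its interval.

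The cost is wording only, since the covariates are already collected and the sample size does not change. The downside is a slightly more complex analysis that depends on the sparse-data rule, so the threshold and covariates must be fixed in advance.

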### **Study design**

This is a 24-week, randomised, double-blind, age-stratified, placebo-controlled, 2-arm, parallel-group, multicentre global Phase III study with a 4-week placebo lead in period and a 28-week extension period I and a 52-week extension period II site-and patient-blinded extension periods. Patients will be stratified according to three factors: age at enrolment (<65 years vs.  $\geq 65$  years), insulin use at randomisation (No vs. Yes), and time from most recent qualifying cardiovascular (CV) event (>1 year versus  $\leq 1$  year).

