**Other secondary outcome variables:**

- Mean change in diastolic blood pressure from baseline to week 24
- Proportion of patients with seated systolic blood pressure <130 mmHg at week 24 in patients who had seated systolic blood pressure  $\geq$ 130 mmHg at baseline
- Mean change in body weight from baseline to week 24
- Mean change in HbA1c in patients with baseline HbA1c  $\geq$ 8.0% and HbA1c  $\geq$ 9.0% from baseline to week 24
- Proportion of patients achieving a therapeutic glycaemic response defined as HbA1c <7.0% at week 24
- Mean change in fasting plasma glucose (FPG) from baseline to weeks 1 and 24
- Proportion of patients rescued for failing to maintain FPG below pre-specified rescue criteria at weeks 4, 8, 16, and 24
- Proportion of patients rescued for failing to maintain blood pressure (systolic and diastolic blood pressure) below pre-specified rescue criteria at weeks 8, 16 and 24
- Proportion of patients achieving a therapeutic response defined as a reduction in HbA1c of 0.5% or more at week 24
- Proportion of patients achieving a reduction from baseline of 3 mmHg or more and 5 mmHg or more in seated systolic blood pressure at week 24
- Mean percent change in fasting lipids (total cholesterol, low-density lipoprotein cholesterol, high-density lipoprotein cholesterol, triglycerides and free fatty acids) from baseline to week 24.
- Mean change in calculated average daily insulin dose from baseline to week 24 in patients treated with insulin at baseline.
- Mean change in health-related quality of life (HRQL) as assessed by the EuroQol-5D (EQ-5D) questionnaire from baseline to week 24

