### **5.2.1 Procedures for randomisation**

Randomisation to investigational products (1:1) will be done via IWRS/IVRS at Visit 4 in balanced blocks in order to ensure approximate balance between the two treatment arms. Patients will be stratified at randomization into one of the 8 age-by-insulin use-by-time from

most recent qualifying CV event strata according to age group (<65 years versus  $\geq 65$  years at enrolment), use of insulin (No versus Yes at randomisation) and time from most recent qualifying CV event (more than 1 year versus 1 year or less (ie, within 12 months) before enrolment) (see Section 3.1.1.4). The trial expects to randomise equal numbers of patients to be enrolled within each age group. However, a moderate degree of imbalance between age strata is permitted (see Section 3.1.1.4). There is no restriction on the number of patients enrolled in each of the insulin use strata or time from most recent qualifying CV event strata.

The IWRS/IVRS will sequentially allocate the investigational products through the AstraZeneca prepared randomisation scheme and provide the randomisation number and the appropriate bottle numbers from Investigational Product Supply (IPS) available at the study centre. The Randomisation numbers will be prepared by the global randomization administrator at AstraZeneca and made available for IWRS/IVRS use.

The randomisation is carried out at the study level by way of a central randomisation within the 8 age-by-insulin use-by-time from most recent qualifying CV event strata and the assigned randomisation number and the associated bottle numbers will not be sequential within a centre. Forced randomisation is not allowed.

The patient should always be provided medication with the bottle number allocated by the IWRS/IVRS. If a patient at any time during the study conduct receives the incorrect randomised treatment, this must be corrected as soon as discovered. Until resolution, the patient should continue taking study medication, but at the latest until the next scheduled visit.

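### The single-variable responder models, including key secondary 4, leave out insulin use and time since the CV event: a small, avoidable loss of precision

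*Supplement*

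**What the plan says.** Protocol section 5.2.1 sets the design: "Patients will be stratified at randomization into one of the 8 age-by-insulin use-by-time" since the qualifying CV event. The synopsis agrees: "Patients will be stratified according to three factors: age at enrolment", insulin use and time since that event.

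Section 12.2.1 then describes three kinds of model:

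- **Continuous endpoints (ANCOVA):** an 8-level stratum term overall, a 4-level term within each age stratum, and a baseline covariate.
- **3-item primary responder endpoint (CMH):** the same strata, overall and within age strata.
- **Single-variable responders:** described for HbA1c below 7%, where "estimates, confidence intervals, and tests will be obtained using this methodology with adjustment for baseline HbA1c and age group". The next sentence, on the working model fitted in each arm, says that response is "first modelled using a logistic regression model with baseline HbA1c as the covariate" and does not mention age group.

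The third method is then extended: "The same method will be applied for analyzing other proportions of patients achieving a pre-defined response derived from a single variable". Key secondary 4, a weight loss of 5% or more among those whose BMI was at least 27 at baseline, is named there as one of them. The list of other secondary outcomes brings in further endpoints of this kind, among them "Proportion of patients achieving a reduction from baseline of 3 mmHg or more and 5 mmHg or more in seated systolic blood pressure". Analyses are repeated within each age stratum. An exact method replaces the model when responders average fewer than 5 per arm.

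**The concern.** Where randomisation is blocked within strata, the arms are balanced on the stratification factors. If those factors predict the outcome, an analysis that omits them does not credit that balance: its standard errors are somewhat too large and its tests slightly conservative. The plan avoids this for the ANCOVA and the CMH test but not for the single-variable responders. Within an age stratum age is constant, so neither remaining factor is represented there.

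The protocol itself suggests that insulin use may be prognostic. Section 3.2.4 associates insulin with better glycaemic control and weight gain, and every insulin user's dose is lowered at randomisation.

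The second issue is which baseline is used. Section 12.2.1 names baseline HbA1c and applies the same method to weight and SBP responders without substituting another covariate. Section 1.4 expects blood pressure to fall most where it starts high, so baseline SBP is the natural covariate for an SBP responder.

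At stake is mainly key secondary 4. It is the last step of a fixed sequence under type I error control, run overall and in each age stratum, and its covariates should be fixed without ambiguity before unblinding.

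**Working it through.** **1. The plan's own responder calculation.** The only one is for the 3-item endpoint within an age stratum (section 12.3): 25% v 10%, two-sided alpha 0.0125, power 90%.

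n per arm = [z(α/2)·√(2p̄(1−p̄)) + z(β)·√(p1(1−p1)+p2(1−p2))]² / (p1−p2)²

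= [2.498·√(2·0.175·0.825) + 1.282·√(0.1875+0.09)]² / 0.15² ≈ 181.

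Then 362/(1−0.037) = 376 and 376/0.40 = 940. All three figures reproduce. No power is stated for key secondary 4, so there is no figure to correct.

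**2. Terms in each model.**

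| Analysis | Age | Insulin use | CV-event time | Baseline covariate |
|---|---|---|---|---|
| Randomisation | yes | yes | yes | – |
| ANCOVA | yes | yes | yes | generic |
| CMH, 3-item endpoint | yes | yes | yes | none |
| Single-variable responders, overall | yes in one sentence, absent from the next | no | no | HbA1c |
| Single-variable responders, within age stratum | constant | no | no | HbA1c |

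**3. Size of the loss.** This was simulated with the augmented estimator of the type the plan cites. For arm A, response Y, allocation share π and per-arm logistic predictions m1 and m0, the estimate is the mean of

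A(Y−m1)/π − (1−A)(Y−m0)/(1−π) + m1 − m0,

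with its standard error taken from the sample variance of those terms.

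Assumptions, none of them in the documents:

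- 50% insulin users and 20% with a recent CV event
- blocks of 4 within the 8 strata
- placebo response near 10% (intercept −2.2) and treatment log-odds 0.6
- age and HbA1c not prognostic
- two-sided alpha 0.05, 3,000 runs, N = 800.

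That N is close to what key secondary 4 might have overall: 940 × 0.963 = 905 in the full analysis set, and 905 × 0.85 = 769 if the protocol's 85% overweight-or-obese figure applied here.

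Power (type I error):

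| Log-odds: each omitted factor / per SD of own baseline | HbA1c + age (as written) | HbA1c + three factors | Own baseline + age | Own baseline + three factors |
|---|---|---|---|---|
| 0 / 0 | 0.8210 (0.0467) | 0.8210 (0.0470) | 0.8203 (0.0460) | 0.8210 (0.0467) |
| 0.5 / 0.2 | 0.8247 (0.0433) | 0.8287 (0.0450) | 0.8270 (0.0427) | 0.8333 (0.0447) |
| 1.0 / 0.4 | 0.7963 (0.0397) | 0.8133 (0.0440) | 0.8063 (0.0393) | 0.8253 (0.0423) |

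- As written against full adjustment, the loss is 0, 0.9 and 2.9 points.
- If each endpoint's own baseline was meant, only the two factors are missing. The loss is then 0.8333 − 0.8270 = 0.6 points and 0.8253 − 0.8063 = 1.9 points.
- The Monte Carlo standard error is about √(0.82·0.18/3000) = 0.007 for power and √(0.05·0.95/3000) = 0.004 for type I error. The analyses share data sets, so differences within a row are more precise than that.
- Type I error never exceeds 0.05. The fully adjusted model also runs a little below it, so only part of the shortfall comes from the covariate choice.

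**4. Cross-check on insulin use.** The share of response variance explained is q(1−q)(p1−p0)²/[p(1−p)]. With q = 0.5 assumed, rates of 15% v 10% give 0.25·0.05²/(0.125·0.875) = 0.6%, and 25% v 5% give 0.25·0.20²/(0.15·0.85) = 7.8%. The standard error shrinks by 1−√(1−R²), which is 0.3% to 4.0%. The protocol restricts neither the insulin share nor gives response rates by insulin use.

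The within-stratum analyses were not simulated separately.

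**The case against.** - **Narrow reach.** The 3-item primary responder endpoint and all continuous endpoints are stratified properly. Of the endpoints affected, only key secondary 4 is confirmatory, and it comes last in its sequence. This stands and limits the weight of the point.
- **The baseline wording may be harmless.** HbA1c is named while an HbA1c endpoint is being described. The ANCOVA paragraph also describes HbA1c and then extends the same method to other variables, and nobody would adjust SBP change for baseline HbA1c on that account. The later text speaks of a baseline covariate in general. A reader might infer that weight and SBP responders are certain to be adjusted for HbA1c. The documents support only that the literal wording says so. The missing factors do not depend on this reading.
- **The SAP could settle it.** Section 12 promises one before unblinding, and none is shown. That is a fair answer on endpoint-by-endpoint baselines. It is weaker for the omitted factors, because the protocol states which adjustments are made rather than leaving them open.
- **Small models are safer with few responders.** The method applies from an average of 5 responders per arm, with a separate fit in each arm. An 8-level term plus a baseline needs 9 parameters per arm. Main effects need 5 overall and 4 within an age stratum. This is a good reason for main effects, and close to the threshold even those would be thin. It is not a reason to omit the factors altogether.

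**Conclusion.** The point holds as an efficiency matter. Two of the three randomisation factors are absent from the single-variable responder models overall, and none is present within an age stratum. The two sentences on adjustment also disagree about age group, and the covariate for weight and SBP responders is unclear.

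The cost is 0 to about 3 points of power. The upper end needs log-odds of 1.0 for each omitted factor and 0.4 per SD of the endpoint's own baseline, with baseline HbA1c uninformative. If the factors are not prognostic, nothing is lost. All these strengths are assumptions.

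A reader might infer a threat to validity: bias, or an inflated error rate for a confirmatory test. That does not follow. The estimator targets the marginal difference in response rates whichever covariates are used, the insulin dose reduction applies to both arms, and the simulated error rate stayed at 0.040 to 0.047 for the model as written. Nor does the point reach the primary responder endpoint.

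**What to change.** Amend the single-variable responder text in section 12.2.1, and carry it into the SAP before unblinding:

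1. In each arm's working logistic model, include the randomisation factors as main effects: age group, insulin use and time since the CV event overall; insulin use and time since the CV event within an age stratum. Main effects keep sparse cells from preventing a fit.
2. State that the baseline covariate is that of the variable defining the response: HbA1c for HbA1c responders, SBP for SBP responders, weight for key secondary 4.
3. Make the adjustment sentence and the logistic-model sentence list the same terms.
4. Keep the existing exact-test fallback for fewer than 5 responders on average per arm.

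The cost is a sentence or two. Every covariate is already collected, and 181 per arm, 376 per smaller stratum and 940 in total do not change.
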